7.6.7 Electrocardiogram

Summary statistics (n, mean, standard deviation, median, minimum, and maximum) will be presented for each ECG parameters and the corresponding changes from baseline by treatment and visit. The baseline value is defined as the last measurement before the first dose. ECG readings will be evaluated by the Investigator and abnormalities, if present, will be listed.

The frequency distribution of subjects' maximum recorded post-dose QTcF, PR, QRS and Δ QTcF will be summarized by treatment group for the following ranges:

- QTcF: $QTcF \leq 450$ msec, $450 \text{ msec} < QTcF \leq 480$ msec, $480 \text{ msec} < QTcF \leq 500$ msec, $QTcF > 500$ msec
- PR: $PR \leq 200$ msec, $PR > 200$ msec
- QRS: $QRS \leq 120$ msec, $QRS > 120$ msec
- Δ QTcF: $\Delta QTcF \leq 30$ msec, $30 \text{ msec} < \Delta QTcF \leq 60$ msec, $\Delta QTcF > 60$ msec

Individual QTcF, PR, QRS or Δ QTcF values meeting the above criteria will be flagged in the data listing.

The following summary tables will be provided:

- Electrocardiogram Summary: Summary Statistics for ECG Values and changes from baseline
- Frequency Distribution of Maximum Post-Dose ECG Interval

The following by-subject listings will be provided:

- Electrocardiogram (ECG) Results: visit, date, study day, heart rate (bpm), interval (PR, QRS, QT, QTC), interpretation of findings.
- Investigator Identified Abnormal ECG Results: visit, date, study day, heart rate (bpm), interval (PR, QRS, QT, QTC), interpretation of findings
- Subjects with Heart Rates and Out-Of-Range ECG Intervals: visit, date, study day, time, heart rate (bpm), interval (PR, QRS, QT, QTcB, QTcF), change from baseline (HR, PR, QRS, QT, QTcB, QTcF).

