- p) Has received natalizumab, efalizumab, or agents that modulate B cells or T cells (eg, alemtuzumab, abatacept, alefacept, or visilizumab) within 3 months of first administration of study medication
- q) Has received Rituximab within 6 months of first administration of study medication.
- r) Has received any systemic immunosuppressants (eg, MTX, azathioprine, cyclosporine, 6-thioguanine, mercaptopurine, mycophenolate mofetil, hydroxyurea, and tacrolimus) or anakinra within 4 weeks of the first administration of study medication
- s) Has received phototherapy or any systemic medications/treatments that could affect psoriasis or PGA evaluation (including, but not limited to, oral or injectable corticosteroids, retinoids, 1,25-dihydroxy vitamin D3 and analogues, psoralens,

sulfasalazine, hydroxyurea, or fumaric acid derivatives) within 4 weeks of the first administration of any study medication

- t) Has used topical medications/treatments that could affect psoriasis or PGA evaluation (including, but not limited to, corticosteroids, anthralin, calcipotriene, topical vitamin D derivatives, retinoids, tazarotene, methoxsalen, trimethylpsoralens, picrolimus, and tacrolimus) within 2 weeks of the first administration of any study medication
- u) Is currently receiving lithium, antimalarials, or IM gold, or have received lithium, antimalarials, or IM gold within 4 weeks of the first administration of any study medication
- v) Has received an experimental antibody or biologic therapy within the previous 6 months, or received any other experimental therapy or new investigational agent within 30 days or 5 half-lives (whichever is longer) of any study medication administration or is currently enrolled in an investigational study

7. Physical and Laboratory Test Findings

- a) Evidence of organ dysfunction or any clinically significant deviation from normal in physical examination, vital signs, ECG or clinical laboratory determinations beyond what is consistent with the target population
- b) Urinalysis findings suspicious of infection (e.g. pyuria, bacteriuria) in a non-contaminated sample collected at screening. Subjects may be rescreened and if deemed eligible may be randomized within 14 days of completing an appropriate course of antibiotic treatment for urinary tract infection.

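### The SAP's table of maximum post-dose ECG intervals counts PR >200 msec and QRS >120 msec without regard to baseline, and no planned output counts by arm the subjects who newly crossed either limit

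*SAP*

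**What the plan says.** SAP 7.6.7 lists a summary table titled "Frequency Distribution of Maximum Post-Dose ECG Interval". It summarises by treatment group the frequency distribution of each subject's "maximum recorded post-dose QTcF, PR, QRS and" change in QTcF. PR is split at 200 msec and QRS at 120 msec. QTcF is split at 450, 480 and 500 msec, and change in QTcF at 30 and 60 msec. The PR, QRS and QTcF ranges carry no baseline condition. Only QTcF has a change category.

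The same section defines a baseline: "The baseline value is defined as the last measurement before the first dose". It plans two other baseline-referenced outputs:

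- A table, "Summary Statistics for ECG Values and changes from baseline", by treatment and visit, with n, mean, standard deviation, median, minimum and maximum.
- A by-subject listing of out-of-range intervals that includes "change from baseline (HR, PR, QRS, QT, QTcB, QTcF").

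Protocol 3.3.2, criterion 7(a), excludes "any clinically significant deviation from normal in physical examination, vital signs, ECG or clinical laboratory determinations beyond what is consistent with the target population". It gives no numeric limit for PR, QRS or QTc.

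In SAP 7.6.8, by contrast, the out-of-range criteria for heart rate and blood pressure require both an absolute value and a change from baseline.

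**The concern.** A subject with a PR of 210 msec before dosing and 210 msec afterwards falls in the >200 msec row whatever the drug does. The row therefore adds baseline prevalence to any new onset. Randomisation is stratified by previous biologic treatment and region only (Protocol 4.4, SAP 2.2), so nothing balances baseline conduction between arms of 42.

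This can mislead in either direction. A chance excess of pre-existing cases on one dose looks like a conduction effect, and an excess on placebo can offset a real one. Safety is a primary objective and ECGs are among the data that inform it (SAP 3.1 and 4.3). With five doses set against placebo, readers will compare these counts by eye even though no test is attached to them.

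**Working it through.** **Inputs**
- Arm size n = 42, with six arms in equal ratio (SAP 5 and 2.2).
- Limits: PR 200 msec, QRS 120 msec (SAP 7.6.7).
- Baseline prevalence p above a limit: not in the documents. Assumed range 1% to 8%, taken to persist after dosing.
- No drug effect, unless stated otherwise.

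**Step 1. Reproduce a stated figure with the same arm size.** SAP 5 gives 34%, 88% and 99% as the chance of at least one event among 42 subjects at 1%, 5% and 10% incidence. The formula 1 − (1 − p)^42 gives 34.4%, 88.4% and 98.8%, which agrees. Read as baseline prevalence, the same formula is the chance that a given arm contains at least one pre-existing case.

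**Step 2. False gap from pre-existing cases alone.** The number per arm is Binomial(42, p). Let b(c) be the probability of c cases on placebo and F the cumulative distribution.
- One given active arm has at least 3 more than placebo: Σ b(c) × [1 − F(c + 2)].
- At least one of five does: Σ b(c) × [1 − F(c + 2)^5].

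| Assumed p | Expected per arm (42p) | One given arm | Any of five arms |
|---|---|---|---|
| 1% | 0.42 | 0.6% | 3% |
| 2% | 0.84 | 2.6% | 12% |
| 3% | 1.26 | 5% | 21% |
| 5% | 2.10 | 10% | 34% |
| 8% | 3.36 | 15% | 44% |

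**Step 3. Effect on a real difference.** Suppose true new onset among subjects at risk is 10% on active and 2% on placebo (assumed). In the planned table each arm's rate is p + (1 − p)q on 42 subjects, where q is the new-onset rate. Counting new onset only, the rate is q on 42(1 − p) subjects. The standardised difference is the difference in rates divided by the square root of the summed binomial variances.

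At p = 5% the planned rates are 0.05 + 0.95 × 0.10 = 14.5% and 0.05 + 0.95 × 0.02 = 6.9%. The difference of 0.076 has a standardised value of 1.14. Counting new onset only, 10% versus 2% on 39.9 subjects gives 1.53.

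| Assumed p | Planned table | New onset only |
|---|---|---|
| 1% | 1.45 | 1.56 |
| 2% | 1.35 | 1.55 |
| 5% | 1.14 | 1.53 |
| 8% | 0.99 | 1.50 |

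**Step 4. Two illustrations.**
- *Apparent difference with no effect.* Four pre-existing cases on active, none on placebo and no new cases read as 4/42 = 9.5% versus 0% in the planned table. The new-onset count is 0/38 versus 0/42.
- *Hidden difference.* Three new cases on active and three pre-existing cases on placebo read as 3/42 = 7.1% in both arms. The new-onset count is 3/42 versus 0/39.

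**Step 5. What the change does not remove.** If true new onset is 5% in every arm with 40 subjects at risk, the same calculation gives at least one active arm 3 or more extra new cases in 33% of trials. At 2% new onset it is 11%.

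**The case against.** The strongest reply is that baseline-referenced ECG information is already planned.

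- The by-visit summaries include the minimum and maximum change, so the largest PR and QRS increase in each arm at each visit will be visible.
- In the out-of-range listing, value minus change gives the subject's baseline. At 5% prevalence this means checking about two subjects per arm.
- Protocol 6.7 requires significant ECG worsening to be recorded as an adverse event, and SAP 7.6.5 tabulates treatment-emergent events by system organ class and preferred term.
- The eligibility criteria remove clinically significant ECG deviations, unstable cardiovascular disease and class III or IV heart failure, so prevalence may be near the low end of the range.
- The table layouts are in a Data Presentation Plan (SAP 9) that is not available here, so a baseline column cannot be ruled out.

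All of this stands, and it limits the weight of the point. What remains is that a maximum change does not say how many subjects crossed a limit, a listing is not a count by arm, and adverse event reporting rests on the investigator's judgement rather than a threshold.

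A reader might go further and infer that the ECG analysis ignores baseline altogether, or that QTcF is affected as much as PR and QRS. The text does not support either reading. The same table carries change categories for QTcF, although a subject at 460 msec before and after dosing is still counted in the 450 to 480 msec row.

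**Conclusion.** The point holds for PR and QRS as a gap in one descriptive table. SAP 7.6.7 mixes pre-existing with new prolongation for these two intervals, and no planned output described in the SAP counts new crossings by arm.

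Its size depends on a baseline prevalence that the documents do not give. The chance of a false excess of 3 or more subjects in at least one active arm runs from about 3% at 1% prevalence to 44% at 8%. For one given arm at 5% it is 10%. At 1% to 2% prevalence the loss of contrast in the Step 3 example is small. In that example even the new-onset count stays below 1.645, so it would not usually give a clear signal by itself.

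It would be tempting to conclude that the primary safety assessment is biased. The documents do not support that. SAP 4.3 bases the assessment on medical review of several sources, no test or decision rule uses this table, and the listing lets a reviewer separate the cases. Efficacy is untouched. This is a worthwhile but optional improvement.

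**What to change.** In SAP 7.6.7, cross-tabulate the maximum post-dose category by the baseline category for PR and QRS, and for QTcF for consistency, by treatment group. Report the number of subjects who moved to a higher category than at baseline, with those in a lower category at baseline as the denominator. Keep the planned counts as the table margins, so that nothing now planned is lost.

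The baseline is already defined, and ECGs are scheduled at screening, Day 1 and every later visit (Protocol Tables 5.1-1 and 5.1-2), so no new data are needed. The cost is one re-programmed table and slightly smaller denominators, for example about 40 instead of 42 per arm at 5% prevalence. The change removes baseline carry-over but not chance variation in new onset.

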7.6.8 Vital Signs and Physical Findings

Vital signs parameters (systolic blood pressure, diastolic blood pressure, heart rate, respiratory rate and body temperature) will be listed. Summaries of vital sign parameters and respective changes from baseline will be provided at corresponding visits by treatment group. Subjects with vital signs outside of a pre-specified range will also be listed.

The following criteria will be used to determine vital sign results that are outside of a pre-specified range, where changes from baseline are based on matched postural positions and are calculated as parameter value - baseline parameter value:

Table 7.6.8-1: Vital Sign Parameter Cut-Off Values

Heart Rate(bpm)	Value > 100 and change from baseline > 30, or Value < 55 and change from baseline < -15
Systolic BP(mmHg)	Value > 140 and change from baseline > 20, or Value < 90 and change from baseline < -20
Diastolic BP(mmHg)	Value > 90 and change from baseline > 10, or Value < 55 and change from baseline < -10
Respiration(breaths/min)	Value > 16 or change from baseline > 10
Temperature (°C)	Value > 38.3°C or change from baseline > 1.6°C

The following summary tables will be provided:

- Vital Signs Summary: Summary Statistics for Vital Signs and Changes from Baseline

The following by-subject listings will be provided:

- Vital Signs by Subject: visit, date, study day, position, blood pressure (mmHg), heart rate (bpm), respiration rate (breaths/min), temperature (°C).
- Subjects with Out-Of-Range Vital Signs: visit, date, study day, position, blood pressure (mmHg) (systolic, diastolic), pulse rate (bpm), respiration rate (breaths/min), temperature (°C), criteria.
- Physical Examination with Abnormal Finding: examine criteria, abnormality.

7.6.9 Other Observations Related to Safety

The following by-subject listings will be provided:

- Medical Treatment Procedures: procedure, start and stop date, reason for procedure.
- Diagnostic Procedures: procedure, date of procedure, reason for procedure, findings.

7.7 Pharmacokinetic Results

The PK analysis will be performed for the Pharmacokinetic Population. Samples for PK assessment will be collected per the Pharmacokinetics Sampling Schedule as described in Table 5.5.1-1 of the study protocol. The summary statistics of BMS-986165 concentrations will be provided by treatment group and nominal visit.

The following summary table will be provided:

- Summary Statistics of Ctrough (mean, SD, geometric mean, % CV, median, min, and max).

The following by-subject listing will be provided:

- Concentration of BMS-986165, including treatment, study day, actual time of sampling, and nominal time. Actual time since previous dose and actual time since Day 1 will be calculated and included in the listing for samples other than Ctrough.

The following graph will be provided:

- Plot of Ctrough over time (Mean +/-SD) by treatment arm.
- Plot of individual Ctrough over time.

[REDACTED]

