3.3.1 Inclusion Criteria

1. Signed Written Informed Consent

- a) Subjects is willing to participate in the study and has signed the informed consent

2. Target Population

- a) Male and female subjects with a diagnosis of plaque psoriasis for ≥ 6 months
- b) Body mass index (BMI) 18-40 kg/m² and total body weight > 50 kg (110 lb)
- c) Deemed by Investigator to be eligible for phototherapy or systemic therapy
- d) Psoriatic plaques must cover $\geq 10\%$ of body surface area (BSA)
- e) Psoriasis Area and Severity Index (PASI) score ≥ 12 and sPGA ≥ 3

3. Age and Reproductive Status

- a) Males and Females, ages 18 or age of majority to 70 years, inclusive
- b) Women of childbearing potential (WOCBP) must have a negative serum or urine pregnancy test (minimum sensitivity 25 IU/L or equivalent units of HCG) within 24 hours prior to the start of study drug.
- c) Women must not be pregnant, lactating, breastfeeding or planning pregnancy during the study period
- d) Women of childbearing potential (WOCBP) must agree to follow instructions for method(s) of contraception for the duration of treatment with study drug(s) BMS-986165 plus 5 half-lives of study drug plus 30 days (duration of ovulatory cycle) for a total of 33 days post-treatment completion
- e) Males who are sexually active with WOCBP must agree to follow instructions for method(s) of contraception for the duration of treatment with study drug(s) BMS-986165 plus 5 half-lives of the study drug plus 90 days (duration of sperm turnover) for a total of 93 days post-treatment completion. In addition, male subjects must be willing to refrain from sperm donation during this time.
- f) Azoospermic males are exempt from contraceptive requirements. WOCBP who are continuously not heterosexually active are also exempt from contraceptive requirements, and still undergo pregnancy testing as described in this section.

Investigators shall counsel WOCBP and male subjects who are sexually active with WOCBP on the importance of pregnancy prevention and the implications of an unexpected pregnancy. Investigators shall advise on the use of highly effective methods of contraception ([Appendix 1](#)) which have a failure rate of < 1% when used consistently and correctly.

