4.5 Selection and Timing of Dose for Each Subject

The BMS-986165 capsules (active or placebo) are provided in blister card kits which contain 48 capsules and will treat the patients for 8 days. The capsules will be arranged in 8 rows each containing four capsules to be taken each morning and two capsules to be taken at night, approximately 12 hours after the morning dose and will contain the appropriate combination of active and placebo to provide the subjects required daily dose (3mg every other day, 3mg every day, 3 mg twice daily, 6 mg twice daily, 12 mg every day, or placebo). It is essential that all patients finish all 8 days of treatment prior to starting a new blister card kit to ensure appropriate doses as identified above. If the subject forgets to take the dose, but remembers within 4 hours of the scheduled dose, then they should take it. If it is past 4 hours, they should miss that dose and take the next scheduled dose. Fasting is not required for drug administration, except on the days scheduled for blood collection under fasting conditions (Days 1, 8, 15, 29, 57 and 85). On these days, the morning dose should be administered at the investigator's site.

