5.5.1 Pharmacokinetics: Collection and Processing

Table 5.5.1-1 lists the sampling schedule to be followed for the assessment of pharmacokinetics. Further details of blood collection and processing will be provided to the site in the procedure manual.

Table 5.5.1-1: Pharmacokinetics Sampling Schedule

Study Day of Sample Collection	Event	Time (Relative To BMS-986165 Dose) Hour: Min	BMS-986165 Blood Sample for PK	Notes
1	predose ^a	00:00	X	
1		00:30	X	
1		01:00	X	
8	Predose ^a	00:00	X	
15	Predose ^a	00:00	X	
15*		00:30	X	*These post-dose samples maybe drawn at any scheduled visit day after Day 15 (i.e On Day 29, 57 or 85)
15*		01:00	X	
15*		04:00	X	
15*		06:00	X	
29	Predose ^a	00:00	X	
57	predose ^a	00:00	X	
85	predose ^a	00:00	X	

^a predose samples must be drawn before the morning dose on the Visit Day

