7.4.1 Administration of Study Therapy

Table 7.4-1 provides the definition of parameters for administration of study therapy.

Table 7.4-1: Administration of Study Therapy: Definition of Parameters

BMS-986165	
Dosing schedule per protocol	3mg Q2D, 3mg QD, 3mg BID, 6mg BID, and 12mg QD
Total Dose	Total dose (mg) is sum of all doses administered during the study
Duration of treatment	Last dose date - Start dose date +1

The following parameters will be summarized (descriptive statistics):

- Number of doses received
- Total dose
- Duration of treatment

The following by-subject listing will be provided:

- Study Drug Administration: visit, date/day of dose, blister card number (flag if drug assigned but not taken), number of capsules per day.

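### In the 3 mg Q2D arm the Day 8 predose sample lies 24 h out of phase with the later four, yet SAP 7.7 tabulates and plots all five as one Ctrough series (minor)

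*SAP*

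**What the plan says.** **Sampling.** Protocol 5.5.1 sets predose samples on Days 8, 15, 29, 57 and 85 for every arm, with no separate rule for Q2D: "predose samples must be drawn before the morning dose on the Visit Day".

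**Dosing.** Under Protocol 4.5 all arms take capsules every day, four in the morning and two at night, from 8-day cards that combine active and placebo. On continuity it says: "It is essential that all patients finish all 8 days of treatment prior to starting a new blister card kit". It does not say which rows, or which time of day, carry the active capsule in the Q2D card.

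**Windows.** Protocol Table 5.1-2 allows ±3 days for visits from Day 8 to Day 57 and ±7 days at Day 85, with no condition on odd or even days.

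**Analysis.** SAP 7.7 states: "The summary statistics of BMS-986165 concentrations will be provided by treatment group and nominal visit". It adds a Ctrough summary table, individual plots and "Plot of Ctrough over time (Mean +/-SD) by treatment arm". Time since the previous dose is handled as follows: "Actual time since previous dose and actual time since Day 1 will be calculated and included in the listing for samples other than Ctrough".

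**Status.** Trough concentration is a secondary objective (SAP 3.2) and Ctrough a secondary endpoint (SAP 4.2).

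**The concern.** A trough is the concentration at the end of a dosing interval. In the QD and BID arms, the sample before the morning capsules always ends an interval. In the Q2D arm it does so only on a day when active drug is due. On the other days it falls in the middle of the 48 h interval, and the capsules last taken may all have been placebo.

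SAP 7.7 calculates time since dose for every sample type except the one where it matters here. Followed as written, the Q2D plot could show a step between Day 8 and Day 15 that comes from the sampling phase and not from any change in pharmacokinetics. If the active rows are the odd ones, the step is a fall.

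**Working it through.** The plan gives no figure to reproduce on this point. The check is a count of days, followed by an illustration of size.

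**Step 1. Does the alternation carry across cards?** A card has 8 × (4 + 2) = 48 capsules, as stated. Eight is even and cards are finished in order, so with one row per day from Day 1 the alternation follows study-day parity. The card row on day d is ((d − 1) mod 8) + 1. For Days 8, 15, 29, 57 and 85 this gives rows 8, 7, 5, 1 and 5: one even, four odd.

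**Step 2. Hours since active drug at the planned predose sample.** Hours = 24 × (visit day − last active day before it) − slot, with slot = 0 for a morning and 12 for an evening active capsule. The packing order is not given, so all four placements are shown.

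| Active rows, slot | Day 8 | Days 15, 29, 57, 85 |
|---|---|---|
| Odd, morning | 24 | 48 |
| Odd, evening | 12 | 36 |
| Even, morning | 48 | 24 |
| Even, evening | 36 | 12 |

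The gap between Day 8 and the other visits is 24 h in every row. The Day 1 post-dose samples, scheduled under the column "Time (Relative To BMS-986165 Dose) Hour: Min", fit a morning active dose on Day 1 (the first row), but do not prove it.

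**Step 3. How many samples are mid-interval?** With 42 subjects per arm and five predose visits there are 42 × 5 = 210 planned Q2D samples. If odd rows are active, the mid-interval ones are Day 8: 42/210 = 20%. If even rows are active, they are the other four visits: 168/210 = 80%.

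**Step 4. Visit windows.** With odd rows active and morning dosing, the allowed days that give a 24 h sample are 3 of 7 at Day 8, 4 of 7 at Days 15, 29 and 57, and 8 of 15 at Day 85. A visit one day off target changes what the sample measures.

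**Step 5. Illustrative size.** The visible text gives no half-life. Inclusion criterion 3d in Protocol 3.3.1 sets contraception for treatment "plus 5 half-lives of study drug plus 30 days (duration of ovulatory cycle) for a total of 33 days post-treatment completion". Five half-lives are therefore counted as 33 − 30 = 3 days. Read as a figure rounded up from more than 2 days, this gives 48/5 = 9.6 h to 72/5 = 14.4 h. Both the range and one-compartment decline are assumptions. The ratio between phases is 2^(24/half-life):

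- 14.4 h: 3.2
- 12 h: 4.0
- 9.6 h: 5.7

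The ratio is the same for a morning or an evening active capsule.

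**Step 6. Mixing within a visit (assumed shares).** Take odd rows active and let a share f of Q2D subjects attend a Day 15 to 85 visit an odd number of days off target. The arithmetic mean relative to the true trough is 1 + f × (ratio − 1); the geometric mean is ratio^f.

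| f | Arithmetic mean | Geometric mean |
|---|---|---|
| 0.10 | 1.22 to 1.47 | 1.12 to 1.19 |
| 0.25 | 1.54 to 2.16 | 1.33 to 1.54 |

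The documents give no figure for f.

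**The case against.** Much can be said in the plan's defence.

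- **Summaries are by nominal visit**, so Day 8 is not averaged with later visits. This stands. The fault lies in labelling and plotting them as one trough series.
- **The raw material is listed.** The concentration listing gives study day and actual sampling time for all samples, and SAP 7.4.1 lists dosing: "Study Drug Administration: visit, date/day of dose, blister card number (flag if drug assigned but not taken), number of capsules per day". A careful reader with the packing key could rebuild the interval. That is true, but SAP 7.7 does not plan it for Ctrough. Extending its time-since-previous-dose column unchanged would not help, because in this arm the previous dose may be placebo.
- **Population PK** (Protocol 8.4.8.1) could use actual times. It is reported separately from the study report, so it does not correct the table and plots there.
- **Text is not all visible.** Blocks after SAP 7.7 and Protocol 8.4.4 are redacted, and the table mock-ups are in a separate Data Presentation Plan. The finding can only be that no visible rule addresses this.
- **The sizes are soft.** They rest on a half-life inferred from a contraception rule, and the arithmetic mean is more sensitive than the geometric mean, which is also planned. This stands; only the 24 h gap is firm.

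A reader might infer that the trial will misreport trough exposure of 3 mg QD relative to Q2D, or that dose comparisons are compromised. The documents do not support this. SAP 7.7 plans no between-arm ratio, test or model of Ctrough, and no visible decision rule uses it. Nor can one infer that the later visits are wrong: if odd rows are active, samples taken exactly on Days 15 to 85 end the interval as they should.

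**Conclusion.** The point holds and is minor. In the 3 mg Q2D arm the planned Day 8 sample differs from the other four by 24 h since active drug under every packing order, given one card row per day from Day 1. SAP 7.7 has no visible rule that separates the two phases. Off-target visits can add mixing within a visit, to an unknown extent.

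The consequence is limited to one arm's descriptive Ctrough table and plots. PASI-75, safety and all planned tests are unaffected. The difference of about 3 to 6 fold between phases is an illustration under the assumed half-life of 9.6 to 14.4 h. Which visits are mislabelled depends on a packing order that the documents do not give.

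**What to change.** In SAP 7.7:

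1. After unblinding, derive time since the last **active** dose for every Q2D predose sample from dose dates, card numbers and the packing key, and add it to the concentration listing. Dates are enough to separate the two phases.
2. In the Q2D table and plots, label as Ctrough only samples at the end of the interval: predose on a day when active drug is due, about 48 h after a morning active dose or 36 h after an evening one. A rule fixed at 48 h alone would empty the table if the active capsule is in the evening slot.
3. Show the remaining samples in a separate mid-interval row or series; do not discard them.

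The cost is SAP text and one derived variable for one arm, with no new data and no visit moved. The downside is fewer samples in the Q2D trough row: about 42 of 210 fewer if odd rows are active and visits are on target, up to 168 of 210 fewer if even rows are active, and a different number if visits are off target. For example, with odd rows active, 25% of the 168 later samples off parity would move a further 42 to the mid-interval row.
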